7.1. Primary Endpoint(s)

The primary endpoint is the Repeatable Battery for the Assessment of Neuropsychological Status (RBANS)[™] Total Scale Index Score .

The RBANS[™] Total Scale Index Score is comprised of the total mean score of the following 5 indexes themselves comprised of 12 subtests:

1. Immediate Memory – List Learning and Story Memory
2. Visuospatial/Constructional – Figure Copy and Line Orientation
3. Language – Picture naming and Semantic Fluency
4. Attention – Digit Span and Coding
5. Delayed Memory – List Recall, List Recognition, Story Memory, and Figure Recall

The rate of decline during the treatment period of the intervention will be compared to placebo using the proportional disease progression model.

 EPAD - 115736	D2.11 Master Statistical Analysis Plan for the EPAD Platform Proof-of-Concept Trial		
	WP2. Statistical/Methodology Engine Room	Version: v2.0 – Final	
	Author(s): [name], [name], [name]	Security: PU	16/36

If the intervention owner requires an additional endpoint for decision making for an intervention, it will be specified in the Intervention Specific Appendix. This will not change the primary endpoint required in the Master Protocol and the Master SAP.

7.2. Intermediate Biomarker Primary Endpoint

Pharmacological interventions will be required to have already demonstrated target engagement, or if this has not been done, target engagement will have to be demonstrated during the course of the study. Failure to do so as determined by pre-specified criteria will lead to that particular Intervention Specific Appendix (ISA) being discontinued. If not demonstrated before participation into EPAD, the Intervention Specific Appendix will create rules to demonstrate target engagement on biomarker relevant to the proposed mechanism of action. Therefore, this endpoint can be optional if target of engagement has been already demonstrated.

7.3. Secondary endpoint(s)

7.3.1. Cognitive endpoints:

- The 5 RBANS™ indices and the 12 subtests comprising the RBANS™.
 - The Following 5 cognitive domains
 - RBANS index Attention/Executive Functioning: Digit Span & Coding
 - RBANS index Verbal Episodic Memory: List Learning & Story Memory
 - RBANS index Delayed Memory: List Recall, List Recognition, Story Recall & Figure recall
 - RBANS index Visuospatial/Constructional: Figure Copy & Line Orientation
 - RBANS index Language: Picture Naming & Semantic Fluency
-
- Dot Counting (NIH EXAMINER)
 - Flanker (NIH EXAMINER)
 - Favourites (University of California, San Francisco)

7.4. Exploratory endpoint(s)

7.4.1. Cognitive endpoints:

- Four Mountains Task (Cambridge Cognitive Neurosciences)
- Supermarket Trolley (University College London)

7.4.2. Other clinical endpoints:

- 30-item Geriatric Depression Scale (GDS-30 items)

 EPAD - 115736	D2.11 Master Statistical Analysis Plan for the EPAD Platform Proof-of-Concept Trial		
	WP2. Statistical/Methodology Engine Room	Version: v2.0 – Final	
	Author(s): [name], [name], [name]	Security: PU	17/36

- State-Trait Anxiety Inventory (STAI)
- Pittsburgh Sleep Quality Index (PSQI)
- Amsterdam Instrumental Activities of Daily Living Questionnaire (Amsterdam-IADL)
- Clinical Dementia Rating Scale- Global Scale (CDR-GS) and Sum of Boxes (CDR-SB)

7.4.3. *Exploratory biomarker endpoints:*

- Cerebrospinal fluid (CSF) biomarkers: beta-amyloid, t-tau, p-tau
- Neuroimaging parameters (Magnetic Resonance Imaging [MRI]): hippocampal and whole brain volume; vascular burden (white matter lesions [WML], infarcts, lacunes, microbleeds, superficial siderosis)

7.5. **Safety endpoint(s)**

Details of any specific safety assessments required for the trial drug will be reported in the Intervention Specific Appendix

7.5.1. *Physical examination*

A physical examination will be carried out as described in the Master Protocol Flow Chart section.

The physical examination will include, but not be limited to, general appearance, skin, neck, eyes, ears, nose, throat, breast, lungs, heart, abdomen, back, lymph nodes, extremities, and nervous system will be performed.

1. Body weight in kg (to the nearest 0.1 kg) will be measured at the visits indicated in the Flow Chart and the same scale will be used for all measurements
2. The height is measured at Visit 1 (screening) only. Height will be measured to the nearest cm. Height data obtained from the LCS can be used for this measure.

7.5.2. *Vital Signs*

Vital signs, including, but not limited to, systolic/diastolic blood pressure (including orthostatic measurement) and supine pulse rate (after 5 minutes rest) will be recorded at all the study visits, including the early End of Treatment Visit and the Follow-up-Visit, as indicated in the Master Protocol Flow Chart section.

Blood pressure and pulse rate including orthostatic measurements will be assessed supine and standing.

Clinically relevant abnormal findings that become apparent following baseline assessments will be reported as (S)AEs. 'Seriousness' will be defined, when required, in the Intervention Specific Appendix.

 EPAD - 115736	D2.11 Master Statistical Analysis Plan for the EPAD Platform Proof-of-Concept Trial		
	WP2. Statistical/Methodology Engine Room	Version: v2.0 – Final	
	Author(s): [name], [name], [name]	Security: PU	18/36

7.5.3. Safety laboratory parameters

The following comprises a minimum laboratory parameter set to be assessed for all interventions (as indicated in the Master Protocol Flow Chart section).

- Haematology: haematocrit, haemoglobin, erythrocyte count, white blood cell count (total and differential: lymphocytes, monocytes, neutrophils, eosinophils, basophiles), platelet count
- Serum chemistry: urea, uric acid, creatinine, creatinine clearance, protein total, albumin, aspartate aminotransferase (AST), alanine aminotransferase (ALT), gamma glutamyl transferase (GGT), alkaline phosphatase, total bilirubin, sodium, potassium, chloride, glucose, total cholesterol, triglycerides, bicarbonate
- Urinalysis: protein, glucose, urobilinogen, blood
- Drug abuse screen test in urine (planned at screening Visits only). The following drugs will be tested: marijuana, cocaine, opiates, methamphetamine, amphetamines, Phencyclidine, benzodiazepine, barbiturates, methadone, ecstasy, and oxycodone.

7.5.4. Electrocardiogram

ECG-recordings will be made at the time points indicated in the Master Protocol Flow Chart section. Additional, intervention specific ECG-recordings (including time points) may be detailed in the intervention specific appendix flow chart.

Twelve-lead ECGs (I, II, III, aVR, aVL, aVF, V1 – V6) will be recorded using equipment provided by a central ECG vendor. The ECG record should include a minimum of 5 heart cycles (beats). The electronic record will be forwarded to a central ECG facility for evaluation. A report must be filed in the subject's records. The ECG provider will transfer the data to the Sponsor or designee. Electrode placement will be performed according to the method of Einthoven/Goldberger (ankles and wrists). At all timepoints, indicated in the Flow Chart, single ECGs will be recorded. ECG recordings at planned time points may be repeated for quality reasons like alternating current artefacts, muscle movements and electrode dislocation.

7.5.5. Suicidal risk assessed by the C-SSRS

Suicidal risk will be assessed in terms of suicidal behaviour and suicidal ideation using the Columbia–Suicide Severity Rating Scale (C-SSRS®).

Potential research participants will be assessed at the screening visit with the aim of excluding those with active moderate or severe symptomatology prior to the Screen Visit, or recent (or current) suicidal or suicide attempt according to the C-SSRS® (baseline/screening version). Potential research participants presenting with any suicidal behaviour or suicidal ideation will be excluded from participation in EPAD.

Subsequently, the C-SSRS® will be performed at every visit after baseline and as shown in the Flow Chart. If there is a positive response of suicide attempt or suicidal ideation by the research participant during the administration of the C-SSRS® during the treatment period, the appropriately qualified

 EPAD - 115736	D2.11 Master Statistical Analysis Plan for the EPAD Platform Proof-of-Concept Trial		
	WP2. Statistical/Methodology Engine Room	Version: v2.0 – Final	
	Author(s): [name], [name], [name]	Security: PU	19/36

clinician will immediately interview the research participant during the clinic visit and determine if the research participant will be discontinued from the trial. Appropriate actions for the research participant's safety will be initiated by the investigator. For assessment of the C-SSRS®, paper forms will be used and results will be transcribed into the e-CRF.

7.5.6. Medical history

Full medical history will be taken for the research participants, including but not limited to:

- Cerebrovascular accident (stroke and/or transient ischemic attack [TIA])
- Seizures (including febrile seizures in childhood) or epilepsy
- Thrombotic conditions, including deep venous thrombosis or pulmonary embolus
- Confirmed myocardial infarction and symptoms of angina
- Congestive heart failure
- Other dementias (e.g., vascular dementia, Dementia with Lewy bodies, and frontotemporal lobar dementia)
- Other central nervous system conditions that may cause progressive deficits in memory and cognition (eg, cerebrovascular disease, Parkinson's disease, Huntington's disease, subdural hematoma, and brain tumor)
- Systemic conditions known to cause dementia (eg, hypothyroidism, Vitamin B12, folic acid deficiency, neurosyphilis, or HIV infection)
- Substance use and abuse
- Major psychiatric illness , not limited to, major depressive disorder, bipolar disorder, anxiety disorder, schizophrenia, and delirium
- Hypertension
- Diabetes
- Medication related side effects: drowsiness, confusion and anorexia
- Falls and syncopes
- Concussion(s) and/or traumatic brain injuries
- Incontinence
- Infections
- Pulmonary disease
- Kidney disease
- Osteoarthritic conditions
- Vision loss

 EPAD - 115736	D2.11 Master Statistical Analysis Plan for the EPAD Platform Proof-of-Concept Trial		
	WP2. Statistical/Methodology Engine Room	Version: v2.0 – Final	
	Author(s): [name], [name], [name]	Security: PU	20/36

- Hearing loss
- Pregnancies.

7.5.7. Adverse events

This includes adverse events covering AE, SAE, AR (adverse reactions), AESI (adverse events special interest), and TLAE (adverse events that are treatment limiting or lead to early discontinuation). See Section 15 for further details on adverse events. The exact safety assessments required for a specific substudy will be outlined in the ISA.

8. Analysis set(s)

Analysis sets will be given a two or three-level name. The first level concerns whether patients were randomized, treated and whether they have valid measurements on the primary outcome (ASRS/ASTS/FAS). The second level concerns which type of control patients are included (ISA-controls/Concurrent-controls/All-controls). For the third level, a qualifier “controls-only” may be added to select only control patients. All sets refer to a single IST but this is not part of the naming. All sets are restricted to subjects within the strata (pre-clinical/pro-dromal; APOe-status) covered by the IST. Other inclusion/exclusion criteria are by default not accounted for, as they may not be assessed in all ISTs. However, an ISA-SAP may specify further restrictions.

The primary efficacy analysis is performed on the set FAS-concurrent controls, with sensitivity analysis on other analysis sets. Poolability of controls is done on the set FAS-concurrent controls-controls only. Safety analyses are done on the set ASTS-concurrent controls.

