8.2. Second level

IST controls: All subjects in all treatment arms in the IST.

Concurrent controls: All subjects in all treatment arms in the IST supplemented with control subjects from other ISTs, defined as follows: The present IST has a First Subject First Visit (FSFV) and Last Subject First Visit (LSFV), and a specified intended study duration. The dates refer to the baseline visit. The placebo subjects contributing from other ISTs are all subjects with a Visit 2 (baseline) date between the dates of the first subject first visit (FSFV) and the last subject first visit (LSFV) in the focus IST(both

 EPAD - 115736	D2.11 Master Statistical Analysis Plan for the EPAD Platform Proof-of-Concept Trial		
	WP2. Statistical/Methodology Engine Room	Version: v2.0 – Final	
	Author(s): [name], [name], [name]	Security: PU	21/36

dates included). Here FSFV and LSFV refer to the baseline visits. Only data from research participants from the strata included in the focus IST are shared. Individual data will be used until the minimum of the study durations of the relevant study and the other study. So, if the actual IST runs over 2 years and the other study over 4 years, only data up to 2 years will be shared. On the other side if the actual IST runs over 4 years and the other study over 2 years, still only data up to 2 years will be shared as further data are not available.

All controls: Defined similar to the concurrent controls, but without the condition of start in PoC between FSFV (inclusive) and LSFV (inclusive). Before unblinding, a cut-off will need to be set regarding the last enrolment day to include. The cut-off date should allow for including data from the Month 6 visit. Research participants who cannot have experienced their Month 6 visit are not included.

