14.1. Secondary endpoints

Each secondary cognitive endpoint will be analysed using the same primary endpoint progression model and a traditional mixed model for repeated measures (MMRM) analysis. Modifications are needed as these are not normalised by sex and age. Thus, assumptions on μ and τ should be re-considered.

 EPAD - 115736	D2.11 Master Statistical Analysis Plan for the EPAD Platform Proof-of-Concept Trial		
	WP2. Statistical/Methodology Engine Room	Version: v2.0 – Final	
	Author(s): [name], [name], [name]	Security: PU	28/36

Subset analyses and additional analyses for each intervention will be specified in the intervention specific SAP.

15. Safety

This section describes only the final analysis. For the interim analyses, only key safety analyses will be performed. If there is a major safety signal, the DSMB will recommend stopping the IST. The interim analyses are covered by the DSMB charter.

AEs will be coded using the Medical Dictionary for Regulatory Activities (MedDRA) coding dictionary. Standard summary tables and listings will be produced. All AEs with an onset between start of treatment and end of the residual effect period (REP). The REP will be defined in the ISA.

All treated patients will be included in the safety analysis. In general, safety analyses will be descriptive in nature and will be based on Sponsor standards. No hypothesis testing is planned.

Statistical analysis and reporting of AEs will concentrate on treatment-emergent AEs. To this end, all AEs occurring between start of treatment and end of the REP will be considered ‘treatment-emergent’. The REP is defined in the ISA. AEs that start before first drug intake and deteriorate under treatment will also be considered as ‘treatment-emergent’.

Frequency, severity, and causal relationship of AEs will be tabulated by system organ class and preferred term after coding according to the current version of the MedDRA.

Laboratory data will be analysed both quantitatively as well as qualitatively. The latter will be done via comparison of laboratory data to their reference ranges. Values outside the reference range as well as values defined as clinically relevant will be highlighted in the listings. Treatment groups will be compared descriptively with regard to distribution parameters as well as with regard to frequency and percentage of patients with abnormal values or clinically relevant abnormal values.

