15.1. Definitions of adverse events

Adverse event (AE)

An adverse event is defined as any untoward medical occurrence in a clinical investigation research participant administered an intervention and which does not necessarily have a causal relationship with this intervention.

An AE can therefore be any unfavourable and unintended sign (including an abnormal laboratory finding), symptom, or disease temporally associated with the use of an intervention, whether or not considered related to the intervention.

 EPAD - 115736	D2.11 Master Statistical Analysis Plan for the EPAD Platform Proof-of-Concept Trial		
	WP2. Statistical/Methodology Engine Room	Version: v2.0 – Final	
	Author(s): [name], [name], [name]	Security: PU	29/36

Adverse Reaction (AR)

An AR is defined as a response to an intervention which is untoward and unintended. Response in this context means that a causal relationship between an intervention and an adverse event is at least a reasonable possibility.

Adverse Events of Special Interest (AESI)

Intervention Specific Appendices may define their AESI, if any, for the intervention and appropriate assessments and monitoring. AESI need to be reported within the same timeframe that applies to SAE.

Serious adverse event (SAE)

A SAE is defined as any AE which:

- results in death of the clinical investigation research participant,
- is life-threatening,
- requires inpatient hospitalisation or prolongation of existing hospitalisation,
- results in persistent or significant disability or incapacity,
- is a congenital anomaly or birth defect,
- any other significant medical event, deemed serious for any other reason when based upon appropriate medical judgment, which may jeopardise the patient and may require medical or surgical intervention to prevent one of the other outcomes listed in the above definitions.

Intensity (Severity) of AEs and SAEs

The intensity (severity) of the AE/SAE will be assessed by the PI and should be judged based on the following:

Mild: Awareness of sign(s) or symptom(s) that is/are easily tolerated, causing minimal discomfort and not interfering with usual activities

Moderate: Enough discomfort to cause interference with usual activity

Severe: Incapacitating or causing inability to work or to perform usual activities

Causal relationship of AEs and SAEs

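### Safety is compared by default only with placebo pooled across intervention trials, using crude frequencies; when the focus trial is the longer one, this can show a false excess of adverse events on active

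*Combined protocol and SAP*

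**What the plan says.** Section 8 of the master SAP gives safety one analysis set: "Safety analyses are done on the set ASTS-concurrent controls". Section 8.2 defines the concurrent-controls level as "All subjects in all treatment arms in the IST supplemented with control subjects from other ISTs". The additions are placebo participants in the same strata whose baseline visit falls within the focus IST's enrolment period. The focus IST's own placebo group is therefore part of the pool.

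Section 8.2 also limits how long shared data are used: "Individual data will be used until the minimum of the study durations of the relevant study and the other study". It works through both directions. A 2-year focus IST uses 2 years from a 4-year IST. In the reverse case, "if the actual IST runs over 4 years and the other study over 2 years, still only data up to 2 years will be shared". The rule governs the shared data; no text shortens the focus IST's own arms.

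Section 15 makes the safety analysis descriptive, includes all treated patients and tabulates adverse events by frequency. The event window runs to the end of the residual effect period (REP), and "The REP will be defined in the ISA". On adverse events of special interest (AESI), Section 15.1 says: "Intervention Specific Appendices may define their AESI, if any, for the intervention and appropriate assessments and monitoring". Section 7.5.7 leaves the exact safety assessments to each intervention-specific appendix (ISA).

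Efficacy is treated differently: "The primary efficacy analysis is performed on the set FAS-concurrent controls, with sensitivity analysis on other analysis sets". Section 14 lists an efficacy analysis on the IST's own controls and a poolability check of the control arms on cognitive progression. Safety has no counterpart to either.

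**The concern.** Only the placebo group inside an IST is randomised against, and blinded with, that IST's active arms. Participants know which IST they are in (Section 5), so blinding does not extend to placebo groups in other ISTs. Once those groups are added, active and placebo can differ in length of observation and in how closely events were sought, without any drug effect.

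A crude percentage with an event rises with follow-up time. If part of the placebo column was observed for 2 years and the whole active column for 4, the placebo percentage is lower for that reason alone. A reader of the final report would see an apparent harm and, from the tables the master SAP specifies, could not tell whether it came from the drug or from the pooling. The parallel table that would separate the two is not required.

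**Working it through.** The documents give no adverse-event rate and no safety sample size, so there is no plan figure to reproduce. The calculation illustrates the mechanism.

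**Inputs from the master SAP.** Focus IST 4 years, other ISTs 2 years (the second example in Section 8.2); shared data cut at the shorter duration (Section 8.2); frequency tables (Section 15); 3:1 allocation (Section 5).

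**Assumptions.** Constant event rate h, the same in everyone; no drug effect; complete follow-up; k other ISTs, each contributing a placebo group as large as the focus IST's own.

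**Formulae.** Risk over t years: p(t) = 1 − exp(−h·t). Pooled placebo: [p(4) + k·p(2)] / (k + 1). False excess: p(4) − pooled placebo.

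For h = 0.10: p(4) = 1 − exp(−0.4) = 0.330 and p(2) = 1 − exp(−0.2) = 0.181.
- k = 1: (0.330 + 0.181)/2 = 0.255, excess 7.4 points.
- k = 2: (0.330 + 2 × 0.181)/3 = 0.231, excess 9.9 points.

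| h per year | Active, 4 years | Placebo at 2 years | Pooled, k = 1 | Excess | Pooled, k = 2 | Excess |
|---|---|---|---|---|---|---|
| 0.05 | 18.1% | 9.5% | 13.8% | 4.3 | 12.4% | 5.7 |
| 0.10 | 33.0% | 18.1% | 25.5% | 7.4 | 23.1% | 9.9 |
| 0.20 | 55.1% | 33.0% | 44.0% | 11.0 | 40.3% | 14.7 |

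**Reverse direction.** Focus IST 2 years, others 4 years: shared data stop at 2 years, every group has p(2), and the excess is 0.

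**Own placebo only.** Both columns have p(4), and the excess is 0.

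**Exposure-adjusted rate on the pooled set.** First events divided by time at risk is p(t) / [p(t)/h] = h in every group. At h = 0.10 both columns show 0.100 per year, and the duration artefact disappears under a constant rate.

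**Event window.** Assume 2 years in all ISTs, h = 0.10, 50 own and 150 shared placebo participants, and a REP of 90 days in the focus IST against 30 days elsewhere. The focus arms show 1 − exp(−0.1 × 2.247) = 20.1% and the shared placebo 1 − exp(−0.1 × 2.082) = 18.8%. The pool is (50 × 20.1 + 150 × 18.8)/200 = 19.1%, an excess of about 1 point. This is small beside the duration effect.

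**Ascertainment, for direction only.** Take 2 years in all ISTs with the same group sizes and h = 0.10, and suppose the other ISTs detect half the events (recorded rate 0.05). Expected first events are 50 × 0.181 + 150 × 0.095 = 23.3. Person-years at risk are 50 × 1.813 + 150 × 1.903 = 376. The pooled rate is 0.062 per year, against 0.100 on active. Exposure adjustment does not repair unequal detection. The one-half is an assumption, and nothing in the documents supports a particular value.

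**The case against.** The strongest reply is that the master SAP contains most of the safeguards already.

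- The duration rule aligns planned follow-up whenever the other ISTs are longer. This stands, so the bias runs in one direction only. The rule leaves the opposite case open, and the master SAP acknowledges it: "still only data up to 2 years will be shared as further data are not available".
- The pool includes the IST's own placebo group, the IST-controls level is already defined, and an ISA may add or restrict sets and overrides the master SAP (Sections 2, 8 and 8.4). This stands too: the own-placebo comparison is not excluded. But it is permitted and not required, so an ISA that is silent inherits the pooled comparison.
- Core ascertainment is common to all ISTs: minimum visits (Section 5), a minimum laboratory panel (7.5.3), centrally evaluated ECGs (7.5.4) and C-SSRS at every visit (7.5.5). The gap is therefore confined mainly to assessments and AESIs that one ISA adds.
- Section 15 relies on sponsor standards, which are not in these documents and might include exposure-adjusted rates or a split of placebo by source. One can say only that the master SAP does not specify them.
- Safety is descriptive, without hypothesis tests, and interim safety monitoring follows the DSMB charter. That limits the consequences but does not correct a biased percentage in the final report.
- Shared controls are a deliberate design feature, and own placebo is small under 3:1 allocation. This is a good reason to keep the pooled table, but not to omit the other one.

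**Conclusion.** The concern holds as a missing default. The only safety comparison named in the master SAP can show a false excess of events on active when the focus IST is longer than the contributing ISTs. In the 4-year against 2-year case, with one or two equal-size other placebo groups, the excess is about 7 to 10 points at an assumed 10% per year, 4 to 6 at 5% and 11 to 15 at 20%. These figures rest on a constant common event rate and complete follow-up; the true size depends on ISA durations and rates not given here. Unequal ascertainment may add to the excess, by an amount that cannot be derived from the documents.

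A reader might infer more, and the documents do not support it:

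- That pooling always distorts safety. It does not through planned duration when the other ISTs are as long or longer.
- That people never assessed for an AESI are counted as event-free. Section 15 gives no denominator rule for such events.
- That another ISA's REP applies to shared placebo. The text does not say whose REP governs, and the REP illustration above is small.
- That a benefit-risk conclusion rests on these tables. No section describes one.

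**What to change.** In Section 8, require by default in every IST a parallel set of safety tables on ASTS-IST controls, a level that Section 8.2 already defines. Keep ASTS-concurrent controls as well; which of the two is called primary is a matter of trade-off.

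In Section 15, for the pooled set:

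- report exposure-adjusted incidence rates, or cut all arms, including the focus IST's own, to a common time window;
- state which REP applies to shared placebo;
- show placebo by source IST beside the pooled column;
- limit pooled comparisons of ISA-specific assessments and AESIs to ISTs that assessed them in the same way.

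The cost is SAP wording and one more set of tables. The own-placebo comparison is less precise. With an assumed 150 active, 50 own and 150 shared placebo participants and an event proportion of 18%, the standard error of the risk difference is √[0.18 × 0.82 × (1/150 + 1/50)] = 6.3 points on own placebo, against √[0.18 × 0.82 × (1/150 + 1/200)] = 4.1 points on the pool. The retained pooled table offsets that loss.
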